In Traditional Chinese medicine, both movement-based and mind-based mind-body practices are known to have homeostatic functions to balance dysfunctional bodily systems. Examining the effects of mind-body practices on circadian cortisol rhythm may shed light on the homeostatic effect of mind-body practices on the dysregulation of the HPA system.

Clinical contributions

The clinical popularity of qigong and mindfulness meditation among local cancer survivors calls for a need for more established evidence on their benefits. Better understanding on culturally popular interventions, in particular, the common and unique effectiveness of different approaches are crucial, as patients and qualified healthcare professionals can select or provide practices which will produce maximum benefits, satisfaction, adherence, and sustainability. This study envisions bringing forth evidence-based mind-body practices which are easily learned, can be self-practiced and incorporated into patients' lifestyles.

Objectives

1. **Primary objective 1** is to study the effectiveness of Baduanjin qigong and Mindfulness mediation for Chinese colorectal cancer (CRC) patients as compared to a no-intervention control independently on:

(1) cancer-related symptoms and symptom distress

(2) mental health

(3) quality of life

(4) biomarkers

(5) mindfulness level

2. **Primary objective 2** is to examine the commonalities and differential effectiveness between two interventions on:

(1) outcome variables

(2) magnitude of change

(3) pace of change

(4) extended compliance

3. **Secondary objective** is to examine the associations between psychological, physical and psychophysical markers and how those relationships change across the time points.

Background of the research

The Reciprocity of the Mind and Body in Cancer

Colorectal cancer impairs patients on multiple levels of well-being. While most physical symptoms can be managed by medication, psychosocial stressors may arise and persist to complicate survival and reduce quality of life of survivors[19]. Patients, especially those who requiring colostomy, suffer from psychosocial trauma including depression, the fear of relapse, altered self-image, loss of social functioning and connections[20]. Local statistics further indicated a high prevalence of elevated depressive symptoms (21.8%)[21].

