1. Baduanjin qigong is more effective than no-intervention control in (i)reducing cancer-related symptoms and symptom distress, (ii)improving mental health, (iii)enhancing quality of life, (iv)positively altering biomarkers, (v)enhancing mindfulness level.

- 2. Mindfulness meditation is more effective than no-intervention control in similar areas and directionality as the above (i) to (v).
- 3. There would be commonalities and differences between Baduanjin qigong and Mindfulness meditation in a)type of outcome variables, b)magnitude of change, c)time when significant outcomes emerge, d)frequency and length of self-practice and long-term compliance.
- 4. The associations among physical and psychological variables as well as psychophysiological biomarkers and the changes of such associations across the time points are exploratory.

Research Plan and Methodology

Research design

This study will utilize a 3-arm randomized controlled trial design with waitlist control. A conceptual model is provided in Appendix A. Upon recruitment, participants will be screened according to the inclusion and exclusion criteria (Appendix B). Baseline data will then be collected. Subsequently, eligible participants will be randomly assigned into one of the 8-week (i)Baduanjin qigong group, (ii)Mindfulness meditation group, and (iii)Waitlist Control group. The Waitlist Control group will continue to receive routine medical care and will have the option to attend either of the interventions after the study is completed. Participants from all 3 arms will be assessed on 4 time points (i)baseline prior randomization, (ii)mid-intervention (4th week), (iii)post intervention (8th week), (iii)6 months post-intervention. Participants will complete the study in 8 months.

Sample size determination, Participant eligibility and Recruitment

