To achieve a statistical power of 0.8 with medium effect size (f2 = 0.25) and significance level of 0.05 in repeated measures MANOVA under the proposed 3-group, 4-time point design, a sample size of 126 is needed. Assuming an attrition rate of about 33.5%, based on prior trials on cancer patients using qigong[8], recruitment of 189 participants (63 per arm) is required. The study population will consist of 189 Chinese-speaking patients aged between 18 and 74, diagnosed with colorectal cancer. Participants will be recruited via posters and newsletters put up at hospital and community organizations servicing cancer patients including Hong Kong Anticancer society. Recruitment will also be done via referral from oncologists. Screening will be conducted after recruitment by a trained research assistant or by the referring medical professional based on the inclusion and exclusion criteria listed in Appendix B.

Intervention groups

Both intervention groups will consist of 8 weekly 90-minute sessions, with a total of 12 contact hours. Interventions will be held in groups of about 10 participants led by 2 trainers qualified for the respective intervention form, one of whom will also be a mental health professional.

a) *The Baduanjin qigong Intervention*[61] consist of eight sequential forms of movements which is practiced with guidance on rhythmic breathing and mindful awareness (see Appendix C for details). Each cycle of the eight movements requires 10 to 15 minutes for completion. Four

cycles will be practiced in each session with short breaks arranged between them. In addition to the in-session practices, participants are encouraged to practice Baduanjin qigong for at least 20 minutes each day and keep a record of their daily practice in a log book.

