(b) *The Mindfulness meditation Intervention* which has been used by co-Is ([name] and [name]) in previous studies is developed based on the core components of the established Mindfulness-Based Stress Reduction and the Mindful Self-Compassion program with adaptation for local practice[57, 62]. The focus of the group is to nurture mindful awareness, acceptance, and self-compassion. The group sessions are composed of a combination of mindfulness-based practice, relaxation, and yoga exercise (Appendix D). The basic philosophy of this intervention is the emphasis of the nurturing of self-kindness attitude, and non-attachment attitude towards inter-personal connectedness and letting go of self-criticism, need for control, and defensive separation in times of adversity. Short breaks will be arranged between each practice. Adjuvant to the in-session practices, participants are recommended to practice the mindful techniques every day for at least 20 minutes while keeping a record of their practice.

(c) Waitlist control group members will continue with routine care and can join either the Baduanjin or Mindful intervention after the 6-month post-intervention assessment.

Ethics

This study will be reviewed by the HKU/HA Institutional Review Board. Written informed consent will be obtained from all participants. To ensure confidentiality, codes will be used to replace names. All data collected will be kept in locked spaces and destroyed 3 years after the study ends. The study will also be registered with the Hong Kong clinical trial registry.

Measurements

Assessments pertain to areas of (i)cancer-related symptoms and symptom distress, (ii)mental health, (iii)quality of life, (iv)biomarkers, (v)mindfulness, (vi)compliance, and (vii)demographic and clinical details. Self-rated scales and salivary cortisol are administered by participants themselves while blood pressure would be measured by the trained research assistant blinded to the randomization. Measurements are taken at all time points except demographic and clinical details.

Cancer-related symptom, symptom distress and quality of life

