- (f) Salivary cortisol. Salivary cortisol collection will be conducted by participants themselves. Saliva samples will be collected at 5 prescribed times (awakening, 45 minutes postawakening, 12:00pm, 5:00pm and 9:00pm) using the collection device, Salivette, which includes a cotton swab to place under the tongue. Smoking, eating and drinking should be avoided and refrained one hour prior to saliva collection. Samples collected will be kept frozen at -20°C.Daily condition measures with salivary cortisol-Measures on participants' health behaviors and activities on the day of saliva collection will be collected along with cortisol. These include (i)sleep quantity that day (hours of sleep at night and nap hours), (ii)subjective sleep quality rated on a scale of 1-10, (iii)smoking habit and the number of cigarettes that day (iv)alcohol/coffee drinking habit and the approximate amount that day, and (v)subjective evaluation of stress levels on the day of collection rated on a scale of 1-10. All the above measures will affect the diurnal cortisol rhythm and must be considered in analysis.
- (g) Blood pressure and heart rate. Following recommended procedures by the Canadian Medical Association[69], blood pressure and heart rates would be measured twice from each arm with a five minute rest intervals between measurements. The four collected readings will be averaged.
- (h) Mindfulness. The Chinese Five Facet Mindfulness Questionnaire (Short form) will be used upon permission. It has 5 domains, observing, describing, acting with awareness, nonjudging to inner experience and nonreacting to inner experience[70]. The 5-point Likert scale has 20 items.

- (i) Compliance. Participants will record their daily duration of qigong or mindfulness meditation practice over the course of the study. This will provide information on the frequency and intensity of practice, and maintenance of self-practice habits after the intervention period.
- (j) Demographics. Participants socio-demographic, such as age, gender, education level, employment status and marital status, as well as clinical profile, including cancer diagnosis, staging, treatment and medication record, onset of mood disturbances if any, critical events around the time of onset, physical exercise habits, complementary treatment used, and psychosocial support service utilization, will be documented based on self-report.

Data analyses

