1. Effectiveness of Baduanjin qigong and Mindfulness meditation (Objective 1 & hypotheses 1&2)

Analysis of variance and chi-square independence tests will be carried out using SPSS to compare the demographic profile of the three groups. The study will use latent growth modeling (LGM) in Mplus 7 [71] to explore the effectiveness of the two mind-body interventions over the four assessment time points, between the respective experimental and waitlist control groups. Traditional analytic techniques such as ANOVA or MANOVA adopt traditional deletion or substitution methods and may not yield precise estimates in the presence of missing data. LGM flexibly analyzes the overall population trajectories using nonlinear modeling such as quadratic growth and the between-person variation in outcome variables, thus allows analysis of all available data via full information maximum likelihood under missing-at-random assumption. This matches the standard intent-to-treat analytic approach of clinical trials with missing data. The level of statistical significance is set at p=0.05, with p-values greater than 0.05 but smaller than 0.10 taken as marginal significance. All models are estimated using the robust maximum likelihood estimator.

2. Commonalities and Differential effectiveness for Baduanjin qigong and Mindfulness meditation (Objective 2 and hypothesis 3).

To examine the commonalities and differential effectiveness for Baduanjin qigong and Mindfulness meditation, treatment effects of the two interventions are directly compared in multigroup conditional growth models. The linear slope factors of the outcomes are contrasted across the two intervention groups via computing the difference in the intercepts of the slope factors between two groups using Model Constraint option. Demographic and clinical characteristics that differed significantly across the three groups in the preliminary analysis are entered as covariates. Influential confounding variables such as clinical prognosis or frequency, intensity and duration of maintenance (compliance) of practice will be controlled.

3. The Mind-body correlations reflected in symptoms and psychophysiological markers (Objective 3 and hypothesis 4).

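### Extended compliance, a primary-objective comparison, is measured only by a self-kept practice record, so non-return may be tied to stopping; a few practice questions put to all active-arm participants would limit this.

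*Combined protocol and SAP*

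**What the plan says.** In the Combined protocol and SAP, Primary objective 2 compares the two interventions, and its list ends with "4) extended compliance". Hypothesis 3 expects commonalities and differences in "frequency and length of self-practice and long-term compliance".

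The data source is described in three places, and each describes the participant's own record:

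- Intervention groups, qigong: participants are encouraged to "keep a record of their daily practice in a log book".
- Intervention groups, mindfulness: daily home practice is recommended "while keeping a record of their practice".
- Measurements, (i) Compliance: "Participants will record their daily duration of qigong or mindfulness meditation practice over the course of the study". The same item relies on this record for maintenance of practice after the intervention ends.

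The opening of Measurements counts compliance among the assessment areas and schedules everything except demographic and clinical details at all four time points. It names no second compliance instrument. Session attendance does not appear among the measurements. Exercise habits do, but under demographics, which are exempt from that schedule.

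On missing data, Data analyses 1 says that growth modelling "thus allows analysis of all available data via full information maximum likelihood under missing-at-random assumption". That section concerns each intervention against waitlist. Data analyses 2 compares the two interventions and uses compliance as a control variable. No section says how compliance is analysed as an outcome, or whether a blank or unreturned record means zero practice or missing data.

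The sample size section assumes about 33.5% attrition overall, taken from prior qigong trials in cancer patients. It gives no figure by arm and none for mindfulness.

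**The concern.** The record has to run through the 8-week programme and the 6 months after it. Someone who stops practising has nothing to enter and less reason to keep or return it. If people behave that way, the event of interest (stopping) makes the outcome less likely to be observed. This would have two consequences:

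- Persistence would be overstated in both arms.
- If such loss were heavier in one arm, that arm could look the more compliant for that reason alone.

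The Clinical contributions section says the trial should help patients and professionals choose practices partly for adherence and sustainability, so this comparison has a practical use. Practice status that is not asked about at the time cannot be reliably recovered later, and analysis alone cannot fully replace it.

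**Working it through.** **1. The plan's attrition figure.** From the sample size section, 126 evaluable with 33.5% attrition: 126 / (1 − 0.335) = 189.5. The stated 189 (63 per arm) implies 1 − 126/189 = 33.3%. The figure is reproduced to rounding. Two active arms give 2 × 63 = 126 people, so about 0.335 × 126 = 42 may be lost from this comparison.

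**2. Worst-case illustration.** The documents give 63 per arm and about one third lost. Everything else is assumed: 28 of 63 (44.4%) still practising at 6 months in both arms, 35 stoppers per arm, every loss a stopper, 16 lost in one arm and 26 in the other, and lost participants contributing nothing.

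- Total loss: (16 + 26)/126 = 33.3%.
- Arm with less loss: 28/(63 − 16) = 28/47 = 59.6%.
- Arm with more loss: 28/(63 − 26) = 28/37 = 75.7%.
- Apparent difference: 16.1 points, where the truth is zero.
- Pooled proportion 56/84 = 0.667; standard error √(0.667 × 0.333 × (1/47 + 1/37)) = 0.104; z = 0.161/0.104 = 1.55, two-sided p about 0.12.

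**3. Equal loss, all among stoppers.** 21 lost per arm: 28/42 = 66.7% in both arms. There is no false difference, but both are overstated by 22 points.

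**4. Loss unrelated to stopping, same 16 v 26 split.** Expected practisers with records are 28 × 47/63 = 20.9 and 28 × 37/63 = 16.4. Available records then show 20.9/47 = 44.4% and 16.4/37 = 44.4%, so there is no bias.

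**5. Counting unknown as not practising, in the setting of step 4.** 20.9/63 = 33.2% v 16.4/63 = 26.1%. This creates a false difference of about 7 points against the arm with more loss.

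**6. A second set of assumed inputs.** The truth is 50% practising in both arms, 63 per arm, average attrition 33.5%, and lost participants contribute nothing. The last column is the share of 20,000 simulated trials in which a two-sided z-test on available records gave a false significant difference.

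| Attrition by arm | Losses among stoppers | Records show | False positives |
|---|---|---|---|
| 33.5% v 33.5% | all | 75% v 75% | 5% |
| 25% v 42% | all | 66.7% v 86.2% | 55% |
| 20% v 47% | all | 62.5% v 94.3% | 96% |
| 20% v 47% | 75% | 56% v 72% | 31% |
| 20% v 47% | 50% (unrelated) | 50% v 50% | 5% |

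A false difference therefore needs unequal outcome-linked loss in the two arms. These figures sit at the upper end, because they ignore anything recovered from partial records.

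**The case against.** The strongest reply is that compliance is scheduled at every time point. A person who has stopped practising but attends at 6 months is due a compliance assessment, so the exposure is mainly among people lost to follow-up, who are missing for every outcome. A returned daily record also shows when practice tapered off. Part of this stands: a reader might infer that the plan has no means of telling a stopper from someone who did not return the record, and that is too strong. But the schedule says when compliance is assessed, not how, and the only method described is the record itself.

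A reader might also infer that the analysis will describe record keepers only. The documents do not support that. The sentence on full information maximum likelihood belongs to the comparison with waitlist, the method uses the partial records of people who later drop out, and no analysis of compliance as an outcome is stated. Earlier entries may reduce the bias. They would not remove it if loss depends on the unrecorded practice itself.

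Finally, the behaviour of stoppers, the split by arm and the yes/no persistence measure in the working are assumptions. Hypothesis 3 speaks of frequency and length of practice as well as long-term compliance. This objection stands in full, so the figures show a mechanism and are not a forecast.

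**Conclusion.** The point holds as a conditional weakness in measurement. A primary-objective comparison rests on one self-kept record over about 8 months, with no second source and no stated rule for its absence. If non-return is linked to stopping, persistence is overstated in both arms, and the between-arm comparison is biased if that loss differs by arm.

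On the assumed worst case the records would show 60% v 76% against a true 44% in both arms. It would be wrong to read that 16-point gap as the expected bias, or to conclude that the arm with more dropout will look better. The documents give only an overall attrition rate, the example makes every loss a stopper and discards partial records, and even then p is about 0.12. The bias between arms is zero if loss is unrelated to stopping, or if loss and its link to stopping are equal in both arms.

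The change is worth making because it is cheap and the information cannot be reliably collected afterwards. The efficacy scales are measured separately and are not affected by this point.

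**What to change.** - At the existing 8-week and 6-month assessments, ask everyone randomised to the two active arms, including those who left the classes and whether or not a record is returned: whether they still practise, days and minutes per week over the past 4 weeks, and, if they have stopped, when. Telephone those who miss the visit.
- Keep the class register as the measure of session attendance.
- Define the outcome in the analysis section: frequency and duration of practice, and persistence at 6 months, compared among all randomised to the active arms. State how blank and unreturned records are treated.
- Report record return by arm.
- Give two sensitivity analyses: unknown counted as not practising, and available records only. Neither should be the main rule. The first penalises the arm with more loss when loss is unrelated to stopping (step 5 of the working); the second overstates persistence when stoppers are lost.

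The cost is a few more self-report items, an attendance sheet, a short call to those who miss a visit (about 42 people across the two arms at the planned attrition) and a few sentences of analysis text. Reported compliance will probably be lower than the records alone would show.

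### Primary objective 2 seeks similarities as well as differences between qigong and mindfulness, but its only assigned analysis is a slope-difference contrast, which cannot show similar magnitude, and comparing when each arm reaches significance does not test pace

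*Combined protocol and SAP*

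**What the plan says.** The Objectives section states that primary objective 2 "is to examine the commonalities and differential effectiveness between two interventions on" four things: the outcomes affected, the size of change, its pace, and continued practice. Study Hypotheses, item 3, turns this into a prediction: "There would be commonalities and differences between Baduanjin qigong and Mindfulness meditation in a)type of outcome variables, b)magnitude of change". Its third element, 3c, is the "time when significant outcomes emerge".

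Data analyses, item 2, is headed for this objective and hypothesis. It opens: "To examine the commonalities and differential effectiveness for Baduanjin qigong and Mindfulness meditation, treatment effects of the two interventions are directly compared". It gives one procedure for both aims: the linear slopes of the two active arms are contrasted "via computing the difference in the intercepts of the slope factors between two groups using Model Constraint option". Covariate adjustment is described, but there is no equivalence margin, confidence-interval criterion or definition of what would count as common. The decision rules stated in Data analyses, item 1, are a 0.05 significance level and a band from 0.05 to 0.10 called marginal.

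Item 1 covers Objective 1. It fits growth models "between the respective experimental and waitlist control groups". Nothing there or in item 2 says how those results bear on commonality.

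**The concern.** A test of a difference has two outcomes: a difference is shown, or it is not shown. The second is not evidence that two effects are alike, whatever the power, and it is weak information when the interval is wide. As written, the plan gives the analyst a way to conclude that the arms differ and no way to conclude that they are similar in magnitude.

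Pace has a related problem. If qigong crosses p<0.05 at week 4 and mindfulness at week 8, their week-4 changes may still be almost identical. If both cross at the same visit, their rates of change may still differ. A difference in significance is not a significant difference. A single linear slope over all four assessments also does not separate magnitude from pace, although the objective lists them as distinct targets.

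At stake is how the comparison between mind-based and body-based practice is reported. Without a stated rule, a non-significant slope contrast can be described as a common effect, or a staggered pattern of p-values as a difference in pace, and nothing in the plan rules out either.

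**Working it through.** **Inputs from the documents.** 126 analysed in total, so 126/3 = 42 per arm; 189 recruited, 63 per arm; attrition 33.5%; power 0.80; alpha 0.05. Assessments are at baseline, week 4, week 8 and 6 months after the intervention. All available data are used by full information maximum likelihood, so the effective number per arm lies between 42 and 63.

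**Assumptions.** Two-sided tests (sidedness is not stated), outcome SD = 1, equal arms, normal approximation.

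**1. The plan's own figure.** A global MANOVA test (Pillai trace) with 3 groups, 4 responses and f = 0.25 (f² = 0.0625) needs N = 125, or 126 as a multiple of 3; power at 126 is 0.807. Attrition: 126/(1 − 0.335) = 189.5, against 189 planned. The total is therefore reproduced with f = 0.25. Taking the printed f² = 0.25 literally gives only about 33 to 39 for the MANOVA variants, so the notation needs correcting. For two equal groups, f = 0.25 corresponds to d = 2f = 0.5, which is why 0.5 SD is used below. This calculation was not made for the qigong–mindfulness contrast.

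**2. Single-visit comparison of the two active arms.** SE = √(2/n); 95% half-width = 1.96 × SE; power = Φ(0.5/SE − 1.96).

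| n per arm | SE | 95% half-width | Power at 0.5 SD | Missed |
|---|---|---|---|---|
| 42 | 0.218 | 0.43 SD | Φ(0.33) = 63% | 37% |
| 63 | 0.178 | 0.35 SD | Φ(0.85) = 80% | 20% |

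Baseline adjustment with an assumed correlation of 0.5 multiplies the SE by √0.75 = 0.866. Power becomes 75% and 90%, so 25% and 10% are missed.

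**3. The planned slope contrast.** Assumed times are 0, 1, 2 and 8 months, with equal within-person correlation ρ, and with or without a random slope whose SD over 8 months is 0.3. Power = Φ(d/(s√(2/n)) − 1.96), where s is the SD of a person's estimated slope scaled to 8 months. For example, ρ = 0.5 without a random slope gives s = 0.909, and with n = 42: 0.5/(0.909 × 0.218) − 1.96 = 0.56, so power is 71%.

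| Scenario | Missed, 42 per arm | Missed, 63 per arm |
|---|---|---|
| Linear gap reaching 0.5 SD at month 8, ρ 0.3–0.5 | 29–46% | 13–29% |
| Same, ρ 0.7 | 10–15% | 2–4% |
| 0.5 SD gap by week 8, then flat, ρ 0.3–0.7 | 32–66% | 15–53% |

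**4. Slope does not isolate pace.** Take an arm whose change is 0, 0.25, 0.5 and 0.5 SD at the four visits. The time deviations from their mean of 2.75 are −2.75, −1.75, −0.75 and 5.25, with sum of squares 38.75. The cross-product is −0.4375 − 0.375 + 2.625 = 1.8125. The slope over 8 months is 8 × 1.8125/38.75 = 0.374 SD. An arm that moves steadily to the same 0.5 SD has a slope of 0.5 SD over 8 months. The faster arm therefore has the smaller linear slope, although both end at the same point.

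**5. What an equivalence criterion would achieve.** With no true difference and margin Δ, power = 2Φ(Δ/SE − 1.645) − 1. At an illustrative Δ = 0.5 SD: 42 per arm, 2Φ(0.65) − 1 = 48%; 63 per arm, 2Φ(1.16) − 1 = 75% (68% and 89% with baseline correlation 0.5). At 0.4 SD: 15% and 45%. At 0.3 SD: 0% and 3%. For 80% power, the analysed number per arm is 69, 108 and 191 for margins of 0.5, 0.4 and 0.3 SD.

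**The case against.** The strongest reply is that commonality need not mean equal size. The Clinical contributions section speaks of effects that the practices share and effects specific to each, and hypothesis 3a concerns which outcomes each one changes. Hypotheses 1 and 2 test both arms against waitlist in the same five areas. If both arms beat waitlist on an outcome, a shared benefit is validly supported without an equivalence test. This stands, and it limits the point to magnitude and pace. What remains is that the plan never makes the link, and shared benefit says nothing about similar size or speed.

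A second reply is that repeated measures and likelihood-based handling of missing data give more power than a single-visit completer comparison. That can be so: at ρ about 0.7, with a gap that grows linearly, few 0.5 SD differences are missed. But if the gap opens early and then levels off, the slope contrast can do worse. The documents give neither the correlation nor the trajectory. In either case, power to detect a difference does not turn non-significance into evidence of similarity.

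Third, a reader might infer that the plan intends to report a null slope contrast as a common effect. Data analyses, item 2, does not say so. It computes a difference, which can be reported with its interval. The plan leaves the misreading open; it does not prescribe it.

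**Conclusion.** The point holds for similarity of magnitude and for pace. The only analysis assigned to primary objective 2 and hypothesis 3 cannot show similar magnitude, and the timing comparison in hypothesis 3c does not test a difference in pace. This follows from the text and does not depend on the power figures.

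The figures show how much a non-significant result would leave open. In the single-visit comparison, the interval reaches 0.43 SD either side with 42 per arm and 0.35 SD with 63, and a true 0.5 SD difference is missed about 37% or 20% of the time. These rest on SD = 1, two-sided 0.05 and no baseline adjustment. For the slope contrast only a wide range can be given.

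Two stronger readings are not supported. One is that half of the primary objective cannot be answered: shared benefit is answerable from the waitlist contrasts, and the difference question keeps its own analysis. The other is that similarity would be wrongly concluded about half the time. At a true difference of 0.4 SD the single-visit test with 42 per arm is indeed non-significant 55% of the time. But 0.4 SD lies inside the illustrative ±0.5 SD margin, so calling the arms similar would not be wrong by that standard. That figure is also not for the planned slope analysis.

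**What to change.** Amend Data analyses, item 2, and the wording of hypothesis 3c:

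1. Define a common benefit as both arms superior to waitlist on the same outcome, using the Objective 1 models.
2. Report the qigong–mindfulness difference with its confidence interval and state that non-significance is not evidence of similarity. Claim similar magnitude only if the 90% interval lies within a justified margin set in advance for a few key outcomes. A result showing neither a difference nor similarity is inconclusive. If no margin can be justified, limit the aim to estimating the difference with its interval.
3. For pace, test the between-arm difference in change from baseline to week 4, and from week 4 to week 8, in place of comparing the visits at which each arm reaches p<0.05. Non-significance there is not evidence of equal pace either.

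No new data or visits are needed. The team must choose the key outcomes, which the plan does not single out, and defend a margin for each. The cost is that more results will be reported as inconclusive: at an illustrative ±0.5 SD margin, unadjusted equivalence power is about 48% with 42 per arm and 75% with 63, and it falls quickly for tighter margins.
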